#### **Cmax (pg/mL)**

Cmax will be the maximum quantifiable plasma concentration post-dose of study drug.

#### **tmax (h)**

tmax will be the earliest actual time in hours post-dose of study drug associated with Cmax.

#### **Clast (pg/mL)**

Clast will be the last quantifiable plasma concentration post-dose of study drug.

#### **tlast (h)**

Tlast will be the actual time in hours post-dose of study drug associated with Clast.

#### **λx (/h)**

The terminal phase elimination rate constant will be calculated using concentrations from the elimination phase (i.e., after tmax). Only quantifiable measurements occurring after Cmax, but not including Cmax, will be considered. If any of these quantifiable concentrations occur after an elimination phase concentration that was below the LLOQ, the concentration will be examined by the pharmacokineticist who will determine if the concentration should be included in the calculation. Any such case will be documented in the Clinical Study Report (CSR).

The terminal phase elimination rate constant will be considered unknown if two or fewer concentrations are available. If three or more concentrations are available, then slopes will be estimated for natural log-concentrations over time. The linear regression slope will be calculated

 PROSOFT Clinical	EP-104IAR-201 Statistical Analysis Plan	Version: Final 1.0
	Date: 14-Jun-2023	Page 30 of 38

using the last three quantifiable measurements, again for the last four measurements, again for the last five, and so on. The absolute value of the slope associated with the fitted line having the largest adjusted  $R^2$  value will be used as the terminal elimination rate constant unless there exists an adjusted  $R^2$  value within 0.0001 of the largest, but utilizes a larger number of points, in which case, the regression with the larger number of points is used. If the unadjusted  $R^2$  value is less than 0.8, then  $\lambda_z$  will be considered unreliable and the  $\lambda_z$  value as well as the associated pharmacokinetic parameters  $t_{1/2}$ ,  $AUC_{0-\infty}$ ,  $AUC_{\%extrap}$ ,  $CL/F$ , and  $V_z/F$  will be reported in the listings but excluded from descriptive and statistical analyses.

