Seven toxicology and toxicokinetic/PK studies have been conducted in beagle dogs, including 1 GLP study in 216 dogs. Single IA doses over a 100-fold range of dose levels from 0.6 mg to 55 mg were generally well-tolerated.

At the highest dose in a GLP dog study (55 mg), no adverse effects were documented for body weights, food consumption, ophthalmology or electrocardiography. Transient (<3 days) observations were made of knee discomfort and skin redness at the dosing site with no pain detectable at palpation recorded on, or after, Day 2; these findings were considered procedure-related and not test item-related. Slight increases of mean neutrophil counts, and slight decreases in mean lymphocyte and eosinophil counts, were observed in both sexes; both effects were reversible. Non-adverse minor but persistent decreases in creatinine and increases in cholesterol were also observed. In this dose there was also a trend for slightly lower adrenal gland weights and slightly higher liver weights; atrophy of the adrenal cortex; and hepatocellular vacuolation (consistent with glycogen deposition), albeit with no impact on liver function tests.

Dogs administered with EP-104IAR up to 55 mg (as well as FP alone and PVA alone at comparable high dose levels) had Mankin scores (a 14-point histologic/histochemical classification of cartilage health (Pritzker, et al., 2006)) equal to zero at all doses and time points. In dogs administered with 1.9 or 5.5 mg of EP-104IAR, there were only minimal, sporadic and transient local and systemic histopathology results. At the 55 mg dose, local effects consisted of granulomatous inflammation associated with the local presence of the test items in the synovial lining and occasionally in the synovial stroma; and degeneration/necrosis.

The key non-clinical PK and toxicological findings for EP-104IAR are:

- FP administered by the intravenous (IV) route is systemically cleared within a matter of days. In contrast, EP-104IAR has a t_{max} on the order of hours to days, then plasma levels decline approximately 6-fold over 60-90 days before entering a prolonged plateau phase for up to 10 months.
- Concentrations of FP in the synovial fluid equilibrate at approximately 2-orders of magnitude greater than in the plasma; measurable levels of FP in the synovial fluid can also be seen for at least 10 months.

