8.1.2 Restricted Therapies

Selected corticosteroids are **permitted with the following restrictions:**

- High-potency topical corticosteroids ([Table 2](#)) may be used when necessary, for up to 5 consecutive days in any location except for the Index knee. Subjects should avoid using topical corticosteroids on more than 5% of their body surface area if possible (e.g., 10 x 10 inches or 25 x 25 cm, half an arm).
- Mid- to low-potency topical steroids ([Table 2](#)) may be used in any location except for the Index knee. Subjects should avoid using topical corticosteroids on more than 5% of their body surface area if possible (e.g., 10 x 10 inches or 25 x 25 cm, half an arm).
- Inhaled and intranasal corticosteroids are not permitted from the start of the Washout period until at least 4 weeks post-dose but may be used after this time.

- Intravitreal corticosteroids are permitted (with no restrictions).

Table 2 Topical Corticosteroid Potency Chart

Class	Examples of Generic Drug Names, Strengths and Formulations
1-2 (High Potency)	Amcinomide (0.1% cream, lotion, ointment) Betamethasone dipropionate (0.05% cream, gel, ointment) Betamethasone valerate (0.1% ointment) Clobetasol propionate (0.05% cream, foam, lotion, ointment, shampoo, solution) Desoximetasone (0.05% gel, 0.25% cream, ointment) Diflorasone diacetate (0.05% cream, ointment) Fluocinonide (0.1% cream, 0.05% cream, gel, ointment) Fluocinonide acetonide (0.2% cream, ointment) Halcinonide (0.1% cream, ointment) Halobetasol propionate (0.05% cream, ointment) Mometasone furoate (0.1% ointment) Triamcinolone acetonide (0.5% cream, ointment)

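### SAP 3.9 accepts a rising terminal slope with R-squared of at least 0.8 as an elimination rate, because it takes the absolute value and never requires the slope to be negative

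*SAP*

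**What the plan says.** The rule is in SAP 3.9, in the entry for the terminal rate constant. Only quantifiable concentrations after Cmax are used. "The terminal phase elimination rate constant will be considered unknown if two or fewer concentrations are available". With three or more, log-linear regressions are fitted "using the last three quantifiable measurements, again for the last four measurements, again for the last five, and so on". The rate constant is then "The absolute value of the slope associated with the fitted line having the largest adjusted" R-squared; if another window comes within 0.0001 of the largest value and uses more points, that window is taken instead.

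Two safeguards follow:

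- If the unadjusted R-squared "value is less than 0.8, then" lambda_z is called unreliable. It and t1/2, AUC0-inf, AUC%extrap, CL/F and Vz/F "will be reported in the listings but excluded from descriptive and statistical analyses".
- If quantifiable values "occur after an elimination phase concentration that was below the LLOQ, the concentration will be examined by the pharmacokineticist", who decides whether to include them.

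Neither safeguard looks at the sign of the slope. Later entries in SAP 3.9 use lambda_z in t1/2, AUC0-inf, AUC%extrap, CL/F and Vz/F. They also use it to estimate the Week 24 concentration for AUC0-24wks when that sample is missing, mistimed or below the limit of quantification and nothing quantifiable follows.

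Protocol 1.2.1 reports that, in the non-clinical studies, plasma levels fell about six-fold over 60-90 days "before entering a prolonged plateau phase for up to 10 months".

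**The concern.** An elimination rate describes falling concentrations. R-squared takes no account of sign, so a steady rise meets the 0.8 threshold as easily as a steady fall, and the absolute value then hides the direction. The subject is summarised with a finite half-life and clearance although the data show no elimination over that window. AUC0-inf gains a tail, Clast/lambda_z, that the data contradict.

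The sampling schedule leaves room for this. The smallest window will usually be Weeks 12, 18 and 24 (days 84, 126 and 168). If human levels flatten at 60-90 days as in the animals, those three points lie at or on the plateau, where chance alone can line them up in an upward direction.

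Pharmacokinetics is a stated secondary objective. SAP 3.9 also tests dose proportionality on AUC without saying which AUC, so AUC0-inf could enter that model.

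**Working it through.** The documents give no numerical value for lambda_z, so there is no planned figure to reproduce. The check applies the written rule to an assumed profile and then to simulated ones.

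**Inputs from the documents.** Sampling at 2 hours, Week 1 (Day 3 in the protocol schedule), and Weeks 2, 4, 8, 12, 18 and 24; windows of the last three or more points after Cmax; largest adjusted R-squared with the 0.0001 tie rule; threshold of 0.8; nominal dose 25 mg.

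**Assumed, not in the documents.** The concentrations, and independent log-normal noise with a CV of 10-40%.

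**Worked profile.** 90, 120, 80, 55, 35, 20, 24, 29 pg/mL. The rule selects the last three points.

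- Slope = (ln 29 − ln 20)/84 = 0.3716/84 = +0.00442 per day; R-squared 0.9999, so it is accepted.
- t1/2 = ln 2/0.00442 = 157 days, for levels that are rising.
- AUC0-t by trapezoids = 6,417 pg·day/mL (no lambda_z involved).
- Clast/lambda_z = 29/0.004423 = 6,556, so AUC0-inf = 6,417 + 6,556 = 12,973 pg·day/mL.
- AUC%extrap = 6,556/12,973 = 50.5%.
- CL/F = 1000² × 25/(12,973 × 24) = 80 L/h.

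A milder rise (20, 22, 25) is also accepted: R-squared 0.993, t1/2 261 days, 60% extrapolated.

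**Wobbling tails.** With the same earlier points, the last three values 20, 24, 20; 22, 18, 21; and 20, 20, 24 give R-squared 0.749, 0.776 and 0.673. All are excluded from the summaries. In each the selected slope is negative, so the absolute value changes nothing.

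**Week 24 fill-in.** The formula is Clast × exp(−lambda_z × gap). With lambda_z = 0.00442 per day, a 7-day gap multiplies Clast by exp(−0.031) = 0.97. A 42-day gap (last sample at Week 18) multiplies it by exp(−0.186) = 0.83, whereas continuing the same rise would give exp(+0.186) = 1.20. The effect is small for a mistimed visit and larger after drop-out. It enters AUC0-24wks only through the last trapezoid.

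**Frequency.** Full sampling, 6,000 simulated subjects per setting. Ranges are over a CV of 10-40%.

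| Assumed shape | Accepted, rising slope (% of subjects) | Rising share of accepted fits | Excluded by threshold |
|---|---|---|---|
| Six-fold fall, flat from day 60 | 15-16% | 44-48% | 64-69% |
| Six-fold fall, flat from day 90 | 3-12% | 4-26% | 20-56% |
| Steady decline, six-fold over 300 days | 0-4% | 0-8% | 1-50% |
| Very slow decline, six-fold over 840 days | 2-9% | 4-31% | 42-56% |

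On the two flat plateaus, the accepted rising slopes have a median half-life between 94 and 444 days and a median extrapolated share of 38-69%. For 150 EP-104IAR subjects, 3-16% is about 5 to 24 people (150 × 0.03 = 4.5; 150 × 0.16 = 24).

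**The case against.** The best defence is that little depends on this. No efficacy test, sample size or safety rule uses lambda_z. Individual parameters are listed, summaries include medians and quartiles, and SAP 3.9 calculates parameters only where estimable, so an alert pharmacokineticist could catch a rising tail. That bears on severity. It does not repair the rule, because the SAP ties estimability to the number of points and reliability to R-squared, and gives the pharmacokineticist discretion only after a value below the limit of quantification.

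Several stronger readings are tempting, and the documents do not support them:

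- A reader might infer that any wobbling tail yields a false half-life. Most are removed by the 0.8 threshold, and where the selected slope is negative the absolute value is harmless.
- A reader might infer that total exposure is wrong in general. AUC0-t does not use lambda_z, and AUC0-24wks uses it only for the Week 24 fill-in.
- A reader might infer that the product makes late rises likely. The plateau is a non-clinical finding. Protocol 1.2.2 and 2.1.2 call the human pharmacokinetics predictable and describe no late rise. Protocol 8.1.2 bars inhaled and intranasal corticosteroids "until at least 4 weeks post-dose but may be used after this time", but as a class, with no expected frequency. Late inhaled use could raise fluticasone levels; its size cannot be judged from the documents.
- A reader might go on to ask for a limit on AUC%extrap, or for AUC0-24wks as the main exposure measure. Those are preferences. The SAP already derives both quantities, and no error in it calls for either change.

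One further objection stands. A sign condition removes only upward noise. On a flat plateau from day 60, 16-20% of subjects pass with a negative slope that is also noise, and they would stay in the summaries.

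**Conclusion.** The rule is wrong as written. A rising terminal phase with R-squared of at least 0.8 is treated as elimination, and the resulting lambda_z, t1/2, AUC0-inf, AUC%extrap, CL/F and Vz/F enter the summaries. The Week 24 fill-in can be affected too. That much follows from the SAP text and needs no simulation.

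How often it would happen is uncertain: roughly 3-16% of EP-104IAR subjects if human levels flatten as in the animals, and 0-4% with a steady six-fold decline over 300 days. A still slower decline falls between (2-9%). These figures rest on assumed noise, assumed profile shapes and complete sampling. The consequence is confined to secondary pharmacokinetic parameters.

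**What to change.** Add one sentence to the lambda_z entry in SAP 3.9: lambda_z is estimable only if the selected slope is negative; otherwise lambda_z, t1/2, AUC0-inf, AUC%extrap, CL/F, Vz/F and any Week 24 concentration based on lambda_z are not estimable. In the worked profile, all of these become not estimable and AUC0-t stays at 6,417 pg·day/mL.

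The costs are small but should be stated:

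- Slightly fewer subjects contribute these parameters.
- Some rising-tail subjects whose Week 24 sample is early or missing will also lose AUC0-24wks. The SAP's remaining fallback needs Clast times the gap to be under 1% of AUC0-t. If the 29 pg/mL sample were taken 7 days early, 29 × 7 = 203 pg·day/mL, against 1% of 6,231.5 = 62. Subjects who fail the R-squared threshold already face this.
- Plateau subjects whose noise happens to slope downward remain, so the summaries are selected in one direction. The number not estimable, and the reason, should be shown beside each affected parameter.

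No new data are needed, and no efficacy analysis changes.

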### **$t_{1/2}$ (h)**

The terminal elimination half-life will be calculated as  $\ln(2)/\lambda_z$ , where  $\ln$  is the natural logarithm.

### **$AUC_{0-t}$ (h•pg/mL)**

$AUC_{0-t}$  will be calculated using the linear trapezoidal method. Pre-dose concentrations will be analyzed as time 0. Concentrations below the LLOQ occurring before the first quantifiable concentration will be analyzed as half the LLOQ. Concentrations below the LLOQ occurring after the first quantifiable concentration will be considered missing. Similar to the calculation of  $\lambda_z$ , if a quantifiable measurement during the elimination phase occurs after an elimination phase concentration that is below the LLOQ, the concentration will be examined by the pharmacokineticist who will determine if the concentration should be included in the calculation.

### **$AUC_{0-24wks}$ (h•pg/mL)**

$AUC_{0-24wks}$  will be calculated using the linear trapezoidal method. Pre-dose concentrations will be analyzed as time 0. Concentrations below the LLOQ occurring before the first quantifiable concentration will be analyzed as half the LLOQ. Concentrations below the LLOQ occurring after the first quantifiable concentration will be considered missing. If there is no Week 24 collection, the Week 24 collection does not occur at precisely 24 weeks post-dose, or the Week 24 result is below the LLOQ, the Week 24 plasma concentration level may be estimated as follows:

- If there are quantifiable plasma concentrations before and after Week 24, then the Week 24 concentration will be estimated using linear interpolation.

	EP-104IAR-201 Statistical Analysis Plan	Version: Final 1.0
	Date: 14-Jun-2023	Page 31 of 38

- If there are no quantifiable plasma concentrations after Week 24, but  $\lambda_z$  is estimable with the unadjusted  $R^2$  being greater than or equal to 0.8, then the Week 24 plasma concentration will be estimated by:

$$\text{Week 24 plasma concentration} = C_{\text{last}} * \exp[-\lambda_z * (24 * 7 * 24 - T_{\text{last}})]$$

Where  $C_{\text{last}}$  is the last concentration used in the calculation of  $AUC_{0-t}$  and  $T_{\text{last}}$  is its associated time (h) post-dose.

- If there are no quantifiable plasma concentrations after Week 24 and  $\lambda_z$  was not estimable or reliable, then  $AUC_{0-24\text{wks}}$  will be analyzed using the result for  $AUC_{0-t}$  if  $C_{\text{last}} * (24 * 7 * 24 - T_{\text{last}})$  is less than 1% of  $AUC_{0-t}$ .
- If none of the above criteria were met, then the Week 24 concentration and  $AUC_{0-24\text{wks}}$  will not be estimated.

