### 3. STATISTICAL METHODOLOGY

#### 3.1 General Principles

All collected study data will be presented in listings. All derivations and statistical analyses will be performed using SAS® software Version 9.4 (or higher) or Phoenix® WinNonlin® Version 8.3 (or higher) (Certara USA, Inc., Princeton, NJ). Prior and concomitant medications/procedures will be coded using World Health Organization (WHO) Drug Dictionary Enhanced March 1, 2021 (or most recent version prior to data base lock). Adverse events will be coded using Medical Dictionary for Regulatory Activities (MedDRA) Version 24.0 (or most recent version prior to data base lock).

Unless stated otherwise, descriptive summaries for continuous variables will include n (number of subjects with non-missing results), mean, standard deviation (SD), median,  $Q_1$ ,  $Q_3$ , minimum, and maximum. For categorical variables, n and percent will be provided. Percentages will be calculated out of the number of subjects in the given sample with a non-missing result.

The primary means of efficacy data collection will be via an electronic patient-reported outcome (ePRO) device. Subjects will be provided with a hand-held device programmed to prompt the subject to record data as required throughout the study. The primary means of non-efficacy data collection will be via the electronic case report forms (eCRFs).

Summaries presented by collection day and/or by time point will be based on scheduled assessments as planned in the protocol except for all WOMAC data (See Section 4.1). Unscheduled assessments will be presented in listings and will not be included in the analyses except for: determination of baseline as described in Section 4.3, ACTH stimulation test summaries (See Section 4.4), and for the derivation of PK parameters.

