### AUC0-∞ (h·pg/mL)

$AUC_{0-∞}$  will be calculated as:

$$AUC_{0-∞} = AUC_{0-t} + \frac{C_{\text{last}}}{\lambda_z}$$

Where  $C_{\text{last}}$  is the last concentration used in the calculation of  $AUC_{0-t}$ .

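### SAP 3.9 extrapolates the Week 24 concentration exponentially but integrates up to it in a straight line, so AUC0-24wks can exceed the same subject's AUC0-infinity

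*SAP*

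**What the plan says.** SAP 3.9 states that AUC0-24wks "will be calculated using the linear trapezoidal method". It then deals with profiles that do not end exactly at Week 24: "If there is no Week 24 collection, the Week 24 collection does not occur at precisely 24 weeks post-dose". An unquantifiable sample at that visit is handled in the same way. Four cases follow.

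- If quantifiable values bracket Week 24, the Week 24 value is interpolated linearly.
- If nothing quantifiable follows Week 24 and lambda_z is estimable with R² of at least 0.8, "then the Week 24 plasma concentration will be estimated by" Clast × exp[-lambda_z × (24×7×24 - Tlast)].
- If lambda_z is unusable, AUC0-t stands in, provided that the possible remainder is below 1% of it.
- Otherwise the parameter is not estimated.

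The same section sets AUC0-infinity to AUC0-t + Clast/lambda_z, where Clast "is the last concentration used in the calculation of" AUC0-t. It also says of AUC0-24wks: "Concentrations below the LLOQ occurring after the first quantifiable concentration will be considered missing". If lambda_z has R² below 0.8, it and the parameters that depend on it, AUC0-infinity among them, "will be reported in the listings but excluded from descriptive and statistical analyses".

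**The concern.** The second case assumes that concentrations follow an exponential from Tlast to Week 24, and then measures the area under a straight line between the two ends. AUC0-infinity takes the area under that exponential itself. So two parameters in one listing treat the same stretch of time differently, from the same Clast and lambda_z. A chord of a convex curve lies above the curve, so AUC0-24wks is the one pushed up. If the gap is long enough, the area to 24 weeks comes out larger than the area to infinity.

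The R² condition does not prevent this, because the extrapolation and the summary of AUC0-infinity share the 0.8 threshold: both values would be summarised for the same subject. The SAP limits neither the length of the gap nor the ratio of the two parameters. Long gaps arise when a subject leaves early, or when later samples fall below the LLOQ and are set to missing. What is at stake is the coherence of the PK tables and a selective upward shift in one exposure measure for those subjects.

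**Working it through.** The documents give no numerical result here, so there is no figure to reproduce. The check compares the SAP's own formulas.

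**Inputs.** Week 24 = 24×7×24 = 4,032 h (SAP 3.9). Late PK samples are at Weeks 8, 12, 18 and 24 (SAP 3.9). The human half-life is not given. For illustration only, Protocol 1.2.1 reports for the non-clinical studies a rapid peak, "then plasma levels decline approximately 6-fold over 60-90 days before entering a prolonged plateau phase for up to 10 months". A 6-fold fall in 60 to 90 days gives a half-life of 60/log2(6) = 23.2 days to 90/log2(6) = 34.8 days, or 3.3 to 5.0 weeks.

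**Step 1: the two tails.** Let D = 4,032 - Tlast, x = lambda_z × D and C24 = Clast × exp(-x).

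- Tail of AUC0-24wks as written: D × (Clast + C24)/2 = (Clast/lambda_z) × x(1 + exp(-x))/2
- Area under the SAP's own exponential: (Clast - C24)/lambda_z = (Clast/lambda_z) × (1 - exp(-x))
- Tail of AUC0-infinity: Clast/lambda_z

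The first exceeds the second for every x > 0.

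**Step 2: the crossing.** AUC0-t is common and cancels, so AUC0-24wks exceeds AUC0-infinity exactly when x(1 + exp(-x))/2 > 1. The root is x = 1.688, and 1.688/ln 2 = 2.44 half-lives.

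**Step 3: size.** Profiles were run through the SAP rules at half-lives of 3.3, 4 and 5 weeks. They assume a Day 3 peak of 100 pg/mL followed by mono-exponential decline. Overstatement is measured against the same AUC0-t plus the exponential area to Week 24.

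| Last quantifiable sample | Gap | Crossing if half-life is below | Segment overstated | Whole AUC0-24wks overstated | AUC0-24wks / AUC0-infinity |
|---|---|---|---|---|---|
| Week 18 | 6 weeks | 2.46 weeks | 6–13% | 0.2–0.3% | below 1 (0.967–0.996) |
| Week 12 | 12 weeks | 4.93 weeks | 22–48% | about 3.5% (3.5–3.7%) | 1.00–1.03 |
| Week 8 | 16 weeks | 6.57 weeks | 38–80% | 12–14% | 1.08–1.14 |

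**Step 4: one case in full.** Half-life 4 weeks, last quantifiable sample Week 12: AUC0-t = 89,867 h·pg/mL, Clast = 13.13, C24 = 1.642, D = 2,016 h.

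- As written: 89,867 + 14,894 = 104,761
- Exponential area to Week 24: 89,867 + 11,142 = 101,009
- AUC0-infinity: 89,867 + 12,734 = 102,601

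The rule as written gives 104,761/102,601 = 1.021 times AUC0-infinity. The consistent formula gives a value below it.

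**Step 5: ordinary completers.** If the Week 24 sample is up to 7 days early, the extrapolated segment is overstated by less than 0.4% at these half-lives, and crossing would need a half-life under 2.9 days.

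**The case against.** The strongest reply is that the rule is not shown to overstate true exposure, which a reader might infer. The straight line lies above the fitted exponential, but the sentence in Protocol 1.2.1 that supplies the half-life also reports a long plateau. Take the decline from dosing, a level plateau from Day 60 or Day 90, a 2-hour peak and the SAP's lambda_z rule. The straight line then falls below the true tail by 4 to 42% if the last sample is Week 8 and by 33 to 42% at Week 12. The exponential formula falls further below, by 30 to 68% and roughly 45 to 55%. This stands: the case for change is consistency with AUC0-infinity, not proven accuracy.

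Other stronger readings also lack support.

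- **A large error for a Week 4 leaver.** The lambda_z rule needs three quantifiable points after Cmax. With scheduled samples to Week 4 that requires the peak to be the 2-hour sample. If the peak is on Day 3, only two points remain and the extrapolation is not made.
- **About 20% of subjects affected.** The planned drop-out covers both arms and the whole study, and PK parameters are summarised only for subjects who received EP-104IAR.
- **Damage to other results.** The comparison with inhaled fluticasone in Protocol 2.1.2 is a pre-trial model prediction. The dose-proportionality model in SAP 3.9 refers to AUC without saying which.
- **A need to drop heavily extrapolated values.** Nothing in the documents sets such a limit, and it would remove early leavers selectively.

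SAP 4.4 appears to bar early-exit samples from analyses, while SAP 3.1 admits unscheduled assessments "and for the derivation of PK parameters". The point does not turn on this, since scheduled samples alone produce it.

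**Conclusion.** The inconsistency is real and follows from the formulas alone. In the second case of the AUC0-24wks rule, the segment is always overstated relative to the SAP's own fitted exponential, and beyond 2.44 terminal half-lives the result exceeds AUC0-infinity.

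The size depends on an assumed mono-exponential decline and a half-life borrowed from dogs. On that basis the effect is material when the last quantifiable sample is about Week 8, small at Week 12 and negligible at Week 18 or for completers. Within the assumed range crossing occurs throughout at Week 8, at Week 12 only for half-lives below 4.93 weeks, and not at Week 18. A longer human half-life would make crossings rarer. How many subjects are affected cannot be worked out from the documents.

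This is a minor correction to a descriptive secondary PK parameter. Efficacy analyses are untouched, and no safety decision is shown to rest on it.

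**What to change.** In the second case of the AUC0-24wks rule in SAP 3.9, replace the trapezoid to the estimated Week 24 point with:

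AUC0-24wks = AUC0-t + (Clast/lambda_z) × (1 - exp[-lambda_z × (4032 - Tlast)])

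Times are in hours; convert 4032 if another unit is used. Keep linear interpolation where quantifiable samples bracket Week 24, and leave the third and fourth cases as they are. The added term is always smaller than Clast/lambda_z, so AUC0-24wks stays below AUC0-infinity for every such subject.

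The cost is one formula. It uses only quantities already derived, needs no new data, and no subject loses a value. No exclusion rule based on the extrapolated share is needed.

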9.2.5.7 Visit 9 (Week 24, Day 169 ±7 days) End-of-Study/Early Exit Visit

The following assessments will be performed at this visit:

- Blood samples for hematology, clinical chemistry, HbA1c, cortisol and PK analyses.
- Urine collection for safety urinalysis, pregnancy test and drugs of abuse.
- **Selected subjects only** - ACTH stimulation test.
- Vital signs.
- Physical exam.
- Exam of Index knee.
- Weight.
- PtGA.
- MDGA.
- WOMAC Index.
- Heath status (SF-36).

- Recording of AEs and changes in conmed use.
- Rescue medication accountability will be performed and unused medication collected.
- Check and collect ePRO device.
- The subject and the blinded Assessor will each be asked which treatment they believe was administered.

Imaging Sub-study (Week 24, Day 169 +14 days)

- Review MRI eligibility criteria
- Urine collection for pregnancy test (if applicable)
- MRI

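### The SAP's AUC0-24wks fall-back rule can leave the parameter missing in on-protocol completers sampled a few days early, more often when the late profile is flat

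*SAP*

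**What the plan says.** SAP 3.9, under AUC0-24wks, invokes its estimation rules when the Week 24 sample is missing, is below quantification, or when "the Week 24 collection does not occur at precisely 24 weeks post-dose". Four rules follow.

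1. Sample on each side of the horizon: "If there are quantifiable plasma concentrations before and after Week 24, then the Week 24 concentration will be estimated using linear interpolation".
2. No later quantifiable sample, but λz has unadjusted R² of at least 0.8: extrapolate from Clast to 4032 h using λz. No limit is set on the length of the gap.
3. "If there are no quantifiable plasma concentrations after Week 24 and" λz is not estimable or reliable: use AUC0-t as AUC0-24wks, provided Clast × (4032 h − Tlast) "is less than 1% of" AUC0-t.
4. "If none of the above criteria were met, then the Week 24 concentration and" AUC0-24wks are left unestimated.

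The λz entry in SAP 3.9 sets the reliability limit: when the unadjusted R² "value is less than 0.8, then" λz and the parameters that depend on it are listed but kept out of the summaries. Week 24 is the last planned PK sample, the one before it is Week 18, and actual sampling times are used.

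Protocol 9.2.5.7 gives the visit window: "Visit 9 (Week 24, Day 169 ±7 days) End-of-Study/Early Exit Visit". With dosing on Day 1, Day 169 is 168 days (4032 h) after dosing, so an in-window sample may be up to 7 days short of the horizon.

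**The concern.** A subject can complete the study, attend Visit 9 in window, give a quantifiable sample and still have no AUC0-24wks. The two routes open to an early sample tend to fail for the same reason. A flat terminal phase leaves little slope for the regression to explain, so R² is more likely to fall below 0.8. The same flatness keeps Clast high relative to AUC0-t, so the 1% condition is harder to meet. Fast decliners usually pass one or the other.

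The product is designed for slow release, and Protocol 1.2.1 reports that in non-clinical work "plasma levels decline approximately 6-fold over 60-90 days before entering a prolonged plateau phase". The subjects at risk are thus those who show the intended behaviour.

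The PK objective runs to 24 weeks, and Protocol 2.1.2 predicts total exposure over that period. When λz is unreliable, AUC0-∞ is already out of the summaries. AUC0-24wks is then the only listed AUC with a common time horizon, since AUC0-t stops at each subject's own Tlast.

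**Working it through.** The documents state no expected loss rate, so there is no plan figure to reproduce.

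**Inputs from the documents.** Horizon 168 days; window ±7 days; R² limit 0.8; 1% limit; at least three points after Cmax for λz, choosing the best adjusted R² over the last 3, 4, 5, … points; sampling at pre-dose, 2 h, and Weeks 1 (Day 3), 2, 4, 8, 12, 18 and 24.

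**Step 1: the 1% rule solved for the gap.** Let d be days early and r = Clast ÷ mean concentration over 0–Tlast. Then AUC0-t = (Clast/r)(168 − d), and rule 3 passes only if r·d/(168 − d) < 0.01, that is d < 1.68/(r + 0.01).

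- Wholly flat, r = 1: d < 1.68/1.01 = 1.66 days.
- To pass at d = 7: r < 1.68/7 − 0.01 = 0.23.

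**Step 2: the fall-then-plateau shape.** Take an exponential 6-fold fall over 75 days, then flat, with peak = 1.

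- 0–75 days: 75 × (1 − 1/6)/ln 6 = 34.9
- 75–168 days: 93/6 = 15.5
- Total: 50.4 peak-days
- The rule's own denominator at 165 days: 34.9 + 90/6 = 49.9, and 3 × (1/6)/49.9 = 1.0%. The limit is therefore reached at 3.0 days early (2.7 days for a 60-day fall, 3.3 days for a 90-day fall).
- Share of the full area missing at 7 days early: 7 × (1/6)/50.4 = 2.3%.

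Clast × gap as a percentage of AUC0-t:

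| Days early | Flat | 6-fold fall over 60–90 days, then plateau |
|---|---|---|
| 1 | 0.6 | 0.3–0.4 |
| 2 | 1.2 | 0.6–0.7 |
| 3 | 1.8 | 0.9–1.1 |
| 5 | 3.1 | 1.5–1.9 |
| 7 | 4.35 | 2.2–2.6 |

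**Step 3: the R² condition.** The λz search may reach back into the declining phase, so a plateau does not always fail it. Without noise and with a last sample at 163 days, the 7-point fit gives R² of 0.71, 0.80 and 0.87 for falls lasting 60, 75 and 90 days. The 75-day case is on the boundary (0.803).

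**Step 4: the whole rule chain simulated.** SAP sampling times were used, with 2,000 profiles per setting. The within-subject CV of 15–35% and the profile shapes are assumptions. Percentage losing AUC0-24wks, by days early:

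- Flat: 53–73% at 2 days, 78–82% at 3–7 days.
- Fall then plateau (75 days): 28–29% at 3 days, 47–59% at 5–7 days.
- Terminal half-life 120 days: 8–46% at 5–7 days.
- Terminal half-life 60 days: 0–14% at 5–7 days.
- Terminal half-life 30 days: 0%.
- Any shape at 1 day early: 0–4%.

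**Step 5: all completers, and the effect on the mean.** This adds assumptions on visit timing (uniform over ±7 days, or SD 3 days) and on between-subject spread in plateau level. Across several such sets, about 2–21% of completers lost the parameter.

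One set lost 2.3–10.9%, with mean plateau fraction 0.206–0.236 in those lost and 0.177–0.180 in those kept. With AUC(p) = 75(1 − p)/ln(1/p) + 93p:

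- AUC(0.206)/AUC(0.177) = 56.9/52.1, about 9% higher.
- AUC(0.236)/AUC(0.180) = 61.6/52.6, about 17% higher.
- Shift in the mean: 0.023 × 9% ≈ 0.2%, up to 0.109 × 17% ≈ 1.9%.

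Direct simulation of the mean gave downward shifts of about 0.04–1.9%.

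**The case against.** The strongest reply is that little is lost. SAP 3.9 ranks none of its 11 PK parameters. AUC0-t and Cmax are still reported for every affected subject, and for a sample 7 days early AUC0-t falls short of the full area by only about 2–4%. The summary is descriptive, the mean moves by under about 2%, and one simulated set had a between-subject CV of about 24%. The loss also needs four things together: an early sample, no later quantifiable sample, an unreliable λz and a failed 1% test. Declining to extrapolate without a reliable slope is a defensible pre-specified convention. All of this stands, and it keeps the point minor.

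Two things remain. First, the convention is uneven: rule 2 extrapolates over a gap of any length once R² reaches 0.8, while rule 4 refuses a few days at a level just measured. Second, the refusals are not random with respect to release rate.

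A reader might infer that the trial's main exposure measure is lost, that subjects are dropped, or that the exposure summary is seriously biased. The documents support none of these. No parameter is called main, only one derived value goes missing, and the shift in the mean is small.

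**Conclusion.** The point holds as a minor one. By the text of SAP 3.9 and the Visit 9 window, a compliant completer can lose AUC0-24wks when the last sample is about 2–7 days early (about 3 days or more for the fall-then-plateau shape), λz is unreliable and the 1% test fails. Slower-release subjects are more exposed to this. The harm is avoidable, non-random loss of data; bias in the mean is small.

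The rule thresholds and the 2–4% of area at stake follow from the documents' limits and the stated shapes. The loss rate of roughly 2–21% does not: human terminal shape, assay noise and actual visit timing are not given, and the plateau shape comes from non-clinical studies. PK is a secondary objective, and no efficacy result depends on this rule.

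**What to change.** Keep the 1% rule and add one clause after it in SAP 3.9:

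*If λz is not estimable or reliable, the 1% condition is not met, and the last quantifiable sample lies within 7 days before 24 weeks post-dose (the Visit 9 window), then AUC0-24wks = AUC0-t + Clast × (4032 h − Tlast).*

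Leave all other cases as not estimated. The clause should be added to the 1% rule and not replace it. Replacement would newly drop subjects with gaps over 7 days whose Clast is very low. For example, with the last quantifiable sample at Week 18 (a 42-day gap), the present rule keeps those with r below 0.01 × 126/42 = 0.03. Losing them would create a selective loss at the low-exposure end.

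The cost is one sentence. A flat fill slightly overstates exposure if levels are still falling, by at most part of a 2–4% segment. Reporting the number of subjects whose value came from each rule would let readers see how often it mattered.
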